## **IV. SUBJECT ENROLLMENT**

#### Methods of Enrollment

Prospective participants for each phase of the study from the LTFU study cohort will be identified via LTFU records and recruited and consented at the CCSS Coordinating Center at St. Jude Children's Research Hospital (Supporting Facility for the LTFU) by LTFU staff. Prospective participants will receive an invitation to the study through email and mail (See LTFU Focus Group, Open Pilot, and Pilot Intervention Recruitment Letters). CCSS participants have consented to be contacted by the study and agreed to email communication by voluntarily providing us with their email address. St. Jude employs a system called Emma to administer and deliver email campaigns. Emma ([myemma.com](http://myemma.com)) is a secure email marketing platform that allows for multi-level campaigns with all or segments of our participants. It allows for contact management, simple HTML template design with piping and logical integration, tracking of email campaign receipts, errors, and opt-outs, and drilling down to review participant level activity. If eligible and interested, prospective participants will read over an enclosed Research Consent Form, which they will have the option to either fill out via an online DatStat survey link (the system that St. Jude Children's Research Hospital uses for LTFU consenting procedures, see Data Management in V. Study Procedures) or to fill out the hard copy of the form and mail it back to LTFU staff at St. Jude Children's Research Hospital. Additionally, participants may also be recruited through telephone, with outreach being done by CCSS Coordinating Center, and a mailed version of the recruitment letter might be sent out, with instructions being provided for how to access the online consent portal. Potential participants will also be able to get more information about the study via a St. Jude website (which will also have a link to the online consent form). Following consent, the assignment of a unique study identification number to each participant, and randomization into intervention vs. control arms for Phase 2, participant information will be sent securely to [name] via SharePoint, an encrypted system used to transfer data. [name] team will lead the focus group scheduling and survey facilitation, while both MGH and University of Utah study staff will

coordinate the navigation intervention. The study interventionist may contact consented participants via telephone and email in to schedule intervention sessions.

### Informed Consent

For the participant focus groups, open pilot, and pilot trial, informed consent will be facilitated by LTFU study staff using an IRB approved consent form for each piece of the study (See Focus Group, Open Pilot, and Pilot Intervention Consent Forms. The consent form will describe the study in detail, including the purpose of the research, clinical procedures, risks and discomforts, benefits, reimbursements, and alternatives to participation. Confidentiality, the right of each subject to request further information, and the right of each subject to withdraw from the study at any time, is fully detailed in each consent form. Patients will be informed via the consent form that they can freely choose not to participate. We will exclude participants who, as determined by the study PI or navigator, are unable to give consent due to psychiatric or cognitive impairment. There will be two separate consenting procedures for Phase 1 of the study. One consenting procedure will be for the focus group participants (n=32), and one consenting procedure will be for the open pilot participants (n=10). For Phase 2 of the study, there will be a single consent form for the pilot randomized trial participants (n=80). The intervention arm participants of Phase 2 (n=40) constitute the Phase 3 participants, so they will be consented for Phase 3 during the Phase 2 consent process. There will be separate consent forms that correspond to the described procedures.

### Intervention Assignment and Randomization

#### Pilot Trial

The CCSS Coordinating Center LTFU study staff will randomly select 80 participants among the LTFU cohort (original and expanded together). To do this, CCSS will use stratified random sampling, where we will divide the sample of LTFU participants into two groups: residing in a Medicaid expansion state or not. Random samples will then be selected from each of the two strata until 80 participants are consented and enrolled. The 80 selected participants will be randomized to either enhanced usual care (n=40), or the health insurance navigation intervention (n=40). After obtaining informed consent, participant information will be sent securely to [name] via SharePoint, an encrypted system used to transfer data. [name] team will lead the pilot trial procedures.

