### III. SUBJECT SELECTION

#### Participants: Inclusion and Exclusion Criteria

LTFU study staff at St. Jude Children's Research Hospital keep updated participant contact records for this study, which allows for participants to be approached for additional research studies. For Phases 1 and 2, the LTFU study staff will recruit a total of approximately 122 participants from the Long-Term Follow-Up Study cohort.

Phase 1 will involve recruitment of 32 participants for four focus groups and approximately 5-10 participants for the open pilot. Phase 1 participants will not be eligible for Phase 2 participation. For the focus group activities of this Phase, participants will be randomly selected stratified according to whether they reside in a state with or without Medicaid expansion, which LFTU staff will determine based on participant addresses available from the LTFU data records.

Phase 2 will involve recruitment of 80 randomly-selected participants for the pilot randomized trial. Participants will be randomly selected stratified according to whether they reside in a state with or without Medicaid expansion, which LFTU staff will determine based on participant addresses available from the LTFU data records.

Phase 3 participants will be recruited from the Intervention Arm of Phase 2 (approximately n=40).

For both Phases, we will exclude participants who : (1) do not have health insurance, (2) are under the age of 18, (3) are unable to give informed consent due to psychiatric or cognitive impairment as determined in consultation with study PI, patient navigator, or oncology social worker, and (4) do not have access to a smartphone, computer or tablet with internet access. Importantly, we will closely document and monitor the

numbers of individuals who are unable to participate given this final criterion, as it will further inform the feasibility of this intervention modality.

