## **V. STUDY PROCEDURES**

	Recruitment and consent	Scheduling activity	Procedures	Data - qualitative	Data – quantitative
Phase 1					
Focus groups	LTFU staff identifies Medicaid vs. not Medicaid from LTFU records;	[name] team receives consented list from LTFU via SharePoint; they set up FG time	MGH runs FG via Zoom; records and transcribes the data	Per grant - Content analyses will be conducted by Drs. [name] and	None collected

	Randomly selects and consents  Goal: 4 FG x 8 people -> 32 or so participants	working with MGH team to schedule		the research assistant	
Open pilot	LTFU staff randomly selects & consents participants  Goal: 5-10 participants	[name] team received consented list from LTFU via SharePoint; [name] team set up sessions with navigator	[name] team collects baseline and FU surveys via REDCap	[name] and/or study navigator and research assistant will conduct analyses	Per grant - [name] will lead the analyses of surveys; will receive additional data from LTFU study as needed (demographics, etc) via SharePoint
Phase 2					
Pilot	LTFU staff identifies Medicaid vs. not Medicaid from LTFU records; Randomly selects; Randomizes Participants after they consent  Goal: 80 participants	[name] team receives consented list from LTFU via SharePoint; [name] team set up sessions with navigator	[name] team collects baseline and FU surveys via REDCap	None collected	Per grant - [name] will lead the analyses of surveys; will receive additional data from LTFU study as needed (demographics, etc) via SharePoint
Phase 3					
Exit interviews	No new recruitment	[name] team will help schedule the interviews	Exit interviews run by Utah team	Content analyses will be conducted by Drs. [name] and [name]	None collected

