#### **Quantitative Data**

For quantitative data, [name] team at HCI will conduct the analyses with input from [name] and her study team, and the LTFU study team. As discussed in Participants, we will sample by Medicaid expansion vs. non-expansion states. All analyses will be weighted using inverse sampling probabilities so that results are representative of the overall LTFU study cohort.

At baseline, all pilot participants will complete a baseline. The HINP navigator will use each participant's baseline survey responses to personalize and individualize sessions. At the 3-month post-program follow-up, participants will complete the Phase 1 survey Outcome questions, which will be asked within the 5-month time frame period after trial enrollment. Participants will also be asked questions below about feasibility and acceptability.

We will use descriptive statistics to report on the following endpoints: intervention feasibility (percent of participants enrolled), acceptability (satisfaction, perceived support) and efficacy (e.g., ACA familiarity, health insurance literacy, intention to adhere to recommended survivorship care, provider communication, and coverage status).

Descriptive statistics will examine group differences at baseline; any imbalances will be adjusted. We will use chi square and independent t-tests to compare end-of-intervention changes in preliminary efficacy outcomes between the two groups. Although a 3-month post intervention follow-up period is brief, we will also conduct exploratory comparisons with other study outcomes to see if trends change in the expected direction. We will compare pre/end-of-treatment, within groups, with paired t-tests. In addition, we will use bivariate statistics to examine sociodemographic and cancer-related factors (type of

diagnosis, age at diagnosis, years since diagnosis, cancer treatment, chronic conditions, cancer treatment (e.g., cranial radiation yes/no, anthracycline exposure yes/no) associated with feasibility, acceptability and preliminary efficacy outcomes.

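### Medicaid-expansion status stratifies the sampling but not, as described, the randomisation, and allocation is fixed before the baseline survey is collected

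*Combined protocol and SAP*

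**What the plan says.** Section III (Participants: Inclusion and Exclusion Criteria) says that for Phase 2 "participants will be randomly selected stratified according to whether they reside in a state with or without Medicaid expansion", with state of residence read from addresses already on file. Section IV (Intervention Assignment and Randomization, Pilot Trial) repeats this: "CCSS will use stratified random sampling, where we will divide the sample of LTFU participants into two groups", and then "Random samples will then be selected from each of the two strata until 80 participants are consented and enrolled". The next sentence is the whole description of allocation: "The 80 selected participants will be randomized to either enhanced usual care (n=40), or the health insurance navigation intervention (n=40". The Phase 2 row of the Section V table adds that the same staff identify the stratum, select, and randomise after consent. It gives no method.

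Section VI (Quantitative Data) weights all analyses by inverse sampling probability. It compares changes between arms with chi-square and independent t-tests, and says "Descriptive statistics will examine group differences at baseline; any imbalances will be adjusted". It gives no threshold, covariate list or model.

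On timing, Section IV (Methods of Enrollment) sets this order before participant information is sent on: "Following consent, the assignment of a unique study identification number to each participant, and randomization into intervention vs. control arms for Phase 2". In the Section V table the receiving "team collects baseline and FU surveys via REDCap". The Quantitative Data paragraph of Section V places that team at the University of Utah.

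**The concern.** Expansion status is the only factor by which the plan stratifies its sample, and it also defines the analysis weights. The rationale section gives non-expansion states as an example of where coverage barriers may persist. The efficacy outcomes include insurance literacy, financial distress, policy familiarity and insurance status, so a link with expansion status is plausible. The staff who randomise already hold the stratum. If the two strata are not used in allocation, the arms of a small trial can differ by chance on a known factor. The stated remedy leaves the analyst to decide after seeing the data whether to adjust and for what.

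Timing is a separate matter. Self-rated confidence at baseline is the reference for the between-arm change comparisons and the paired tests. If a participant knows the arm when answering, that reference may be affected by allocation. Someone who learns the arm and never returns the baseline survey becomes a post-randomisation loss.

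**Working it through.** **Plan's own figure.** 40 + 40 = 80, which agrees. No alpha, power, effect size or SD is stated, so there is no power calculation to reproduce.

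**Inputs.** From Section IV: N = 80, with 40 per arm. Assumed, because the documents do not give them: K = 20 to 40 people in the smaller stratum, and a stratum effect g = 0.2 to 0.8 SD on the analysed outcome. For change scores, g is the difference between strata in change.

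**Chance imbalance under unstratified 40:40 allocation.** The number X from a stratum of size K who fall in one arm is hypergeometric (80, K, 40). The gap between arms in stratum share is |2X − K|/40. Its SD is (2/40) × √[40 × (K/80) × (1 − K/80) × 40/79]. For K = 40 this is 0.05 × √5.063 = 0.1125, or about 11 points.

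| K | SD of gap | P(gap ≥ 10 points) | P(gap ≥ 20 points) | P(gap ≥ 25 points) |
|---|---|---|---|---|
| 40 | 11.3 points | 50.3% | 11.7% | 4.4% |
| 28 | 10.7 points | 48.2% | 10.0% | 3.4% |
| 24 | 10.3 points | 46.5% | 8.7% | 2.7% |
| 20 | 9.7 points | 43.9% | 6.9% | 1.9% |

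For K = 40, a 20-point gap is a 24/16 split or worse.

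**Effect on the contrast.** Shift = gap × g. At 20 points: 0.20 × 0.2 = 0.04 SD, 0.20 × 0.5 = 0.10 SD, 0.20 × 0.8 = 0.16 SD. The standard error of the arm difference is √(2/40) = 0.224 SD.

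**Precision.** With equal strata and total SD of 1, stratum explains g²/4 of the variance. Removing it multiplies the SE by √(1 − g²/4).
- g = 0.2: √0.99, a cut of 0.5%.
- g = 0.5: √0.9375, a cut of about 3%.
- g = 0.8: √0.84, a cut of about 8%.

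**Do the sampling weights remove the gap?** No. Take equal strata in the sample, a 24 v 16 split, and an assumed cohort share of 60% in expansion states, so the weights are 1.2 and 0.8. The weighted shares are 28.8/41.6 = 69.2% and 19.2/38.4 = 50.0%, a gap of 19 points. At a 70% cohort share (weights 1.4 and 0.6) they are 33.6/43.2 = 77.8% and 22.4/36.8 = 60.9%, a gap of 17 points.

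**After stratified blocking.** The count difference within a stratum is at most half the block size. Blocks of 4 give at most 2 people, about 2/40 = 5 points; blocks of 6 give at most 3, about 7.5 points. The chance of a gap of 10 points or more falls from 44–50% to zero, with N unchanged.

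**Timing.** No arithmetic applies. The order in Methods of Enrollment is consent, study number, randomisation, then transfer of information. The team receiving that information collects the baseline survey. Allocation is therefore fixed before baseline. No section says when participants are told their arm.

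**The case against.** A reader might infer that the protocol states the 80 are randomised as a single pool. It does not. It gives a 40/40 split and no method, and the Section V table puts stratum identification and randomisation in the same cell, done by the same staff. What the text supports is that stratification is described for sampling only.

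A reader might also infer a bias in the efficacy comparison. Unstratified randomisation is valid. At g = 0.5 a 20-point gap shifts the contrast by 0.10/0.224 = 45% of its standard error, but that is conditional on an event of 7% to 12% probability, and such variation is already inside the standard error. The planned comparison is of changes, so stable differences in level between strata cancel. Only a stratum difference in change would matter, and the documents give no figure for one. Excluding uninsured people narrows one route by which expansion status could act.

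Adjustment for stratum also recovers nearly all of the loss. With equal strata and a 20-point gap, the variance factor is 1/(1 − 0.2²) = 1.042, about 2% on the SE, and the shift is removed if the treatment effect is common to both strata. All of this stands, and it limits the size of the point. What it does not answer is that the plan's adjustment is unspecified and conditional on an observed imbalance, while the named tests have no covariate term.

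On timing, a reader might infer that baseline answers are contaminated by knowledge of the arm. Allocation being set is not the same as its being known, and no section says that participants learn their arm before the survey. The gap is that nothing prevents it.

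**Conclusion.** The point holds as a minor to moderate one. As written, expansion status is used to sample and to weight but not to allocate, and handling of imbalance is left to an undefined rule. The consequence is chance imbalance and a modest loss of precision: a 7% to 12% chance of a gap of at least 20 points (smaller stratum assumed 20 to 40), a shift of 0.04 to 0.16 SD if that gap occurs, and an SE about 0.5% to 8% larger than it need be with equal strata (stratum effect assumed 0.2 to 0.8 SD). The timing point rests on the documented order of steps and carries no estimate of size.

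The rating stays low because the Outcomes section makes feasibility and acceptability primary, and the sample size is justified by feasibility and exploration. It is not negligible, because Aim 2 calls insurance literacy and financial distress primary and states a between-arm hypothesis.

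**What to change.** 1. In Section IV, state that participants are randomised 1:1 within each Medicaid-expansion stratum from a concealed, computer-generated permuted-block list with varying block sizes. If this is already intended, the protocol only needs to say so.
2. In Section VI, pre-specify stratum as a term in the between-arm efficacy model regardless of observed balance, in place of the open-ended adjustment sentence.
3. Release each allocation to the participant and the Utah team only after the baseline survey is returned.

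The cost is a two-stratum list in place of one, with no change in N. Incomplete final blocks may leave the arm totals slightly off 40/40. Holding the allocation adds one message between St. Jude and Utah and a wait before sessions start, which is longer for participants who return the survey by mail.

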## **V. STUDY PROCEDURES**

	Recruitment and consent	Scheduling activity	Procedures	Data - qualitative	Data – quantitative
Phase 1					
Focus groups	LTFU staff identifies Medicaid vs. not Medicaid from LTFU records;	[name] team receives consented list from LTFU via SharePoint; they set up FG time	MGH runs FG via Zoom; records and transcribes the data	Per grant - Content analyses will be conducted by Drs. [name] and	None collected

	Randomly selects and consents  Goal: 4 FG x 8 people -> 32 or so participants	working with MGH team to schedule		the research assistant	
Open pilot	LTFU staff randomly selects & consents participants  Goal: 5-10 participants	[name] team received consented list from LTFU via SharePoint; [name] team set up sessions with navigator	[name] team collects baseline and FU surveys via REDCap	[name] and/or study navigator and research assistant will conduct analyses	Per grant - [name] will lead the analyses of surveys; will receive additional data from LTFU study as needed (demographics, etc) via SharePoint
Phase 2					
Pilot	LTFU staff identifies Medicaid vs. not Medicaid from LTFU records; Randomly selects; Randomizes Participants after they consent  Goal: 80 participants	[name] team receives consented list from LTFU via SharePoint; [name] team set up sessions with navigator	[name] team collects baseline and FU surveys via REDCap	None collected	Per grant - [name] will lead the analyses of surveys; will receive additional data from LTFU study as needed (demographics, etc) via SharePoint
Phase 3					
Exit interviews	No new recruitment	[name] team will help schedule the interviews	Exit interviews run by Utah team	Content analyses will be conducted by Drs. [name] and [name]	None collected

### Data Management, Collection, and Transfer

#### *Recruitment*

During the recruitment periods of each phase of the study, St. Jude will track and obtain consent through DatStat, which allows researchers to configure online mobile responsive web surveys with tailored logic checks and requirements, data pre-populating and piping, and portal access for quick reporting, analytics, and downloads. The system is HIPAA compliant and fully validated for 21 CFR Part 11. Once participants are consented to the study, their information will be sent to [name] and her team at the Huntsman Cancer Institute at the University of Utah via SharePoint. SharePoint is a secure file sharing service supported by the Huntsman Cancer Institute that is encrypted and HIPAA certified. It is password protected and Dr.

[name]'s SharePoint file sharing can only be accessed by other investigators through invitation to ensure data privacy.

#### *Quantitative Data*

For the pilot trial, [name] staff at the Huntsman Cancer Institute at the University of Utah will oversee the scheduling participants and will ensure the completion of the baseline survey and follow-up surveys for both Phase 1 and 2 of the study. Survey data will be collected via a secure web-based portal (REDCap). REDCap is maintained by the bioinformatics shared resource at the Huntsman Cancer Institute where [name] is an investigator. As such, she has access to survey and database support for REDCap for all data collection activities. Data transmissions will occur between [name] and the CCSS Coordinating Center and Statistics and Data Center via SharePoint to facilitate data access from the LTFU baseline and follow up surveys for inclusion in the statistical analysis (<https://ccss.stjude.org/documents/original-cohort-questionnaires>). [name] will lead the pilot study survey data management and analyses, and transmit analytic data to MGH using SharePoint. Data will be managed and cleaned by [name] data manager and overseen by [name].

#### *Focus Group and Exit Interview Qualitative Data*

Once the focus groups are scheduled by [name] team, the data collection efforts will be led via MGH's Zoom program. The Phase 1 participant qualitative data will be collected and stored within MGH. Data will be collected by [name] team at Massachusetts General Hospital using recording devices. Audio recording files will be saved and uploaded into NVIVO software on Shared File Areas in the Partners network, which will only be accessible to IRB-approved study staff. NVIVO files will be sent securely via Partners Secure File Transfer or via SharePoint, which has been approved for use in this study. The Phase 3 qualitative data in the form of exit interviews will follow procedures detailed in Phase 1.

